5.2. Primary endpoint

Percentage of wounds healed within 14 days ($\geq 95\%$ reepithelialisation)

Additional assessments

- Use of antibiotics and antiseptic since last visit

[figure not shown]
Safety assessments

[figure not shown]
- Adverse events
- Device deficiencies

5.4. Rationale for selection and measurement of endpoints

The Primary endpoint percentage of wounds healed within 14 days has been selected for this investigation.

The endpoint is used to evaluate clinical performance in terms of percentage of wounds achieving healing within 14 days (+/- 2 days). Complete healing is defined as $\geq 95\%$ reepithelisation.

Additional assessment

Use of antibiotics and antiseptics

Use of antibiotics and antiseptic will be evaluated to justify any antimicrobial effect observed is due to the test product and not the antibiotic or antiseptics.

Subject will be instructed to document on the sheet for dressing change if any use of antiseptics in the study wound between the scheduled visits, or if they don't know. If subject has used antibiotic or antiseptic, the reason for use and type used will be registered by the PI or delegate at V2 or V3.

Safety assessments

Adverse events and device deficiencies

Will be collected to ensure safety of the intervention during the investigation

5.5. Demography and potential compromising factors

The following baseline data will be collected and reported at the baseline visit by the PI or delegate.

- Age (years)
- Weight (kg)
- Height (cm)
- Gender (male/female)
- Nutritional status (well-nourished, malnourished)
- Mobility status (good mobility, bad mobility)
- Smoking (yes/no)
- Alcohol (Units/week)
- Comorbidities (That can affect wound healing (diabetes, venous insufficiency, peripheral arterial disease, cardiopulmonary conditions, immune deficiencies, dementia, other) or none as deemed relevant by investigator)
- Relevant concomitant medication that can impact wound healing (NSAID, Glucocorticoid steroids and chemotherapeutic drug)
- Use of antiseptics in study wound within the last week and reason for use

Wound description

- Duration of wound
- Previous wound treatment (if applicable)
- Wound size (photo)
- Wound location (upper extremity, lower extremity- leg, lower extremity-foot, abdomen, thorax, back, buttock/sacrum, other)
- Reason of burn (thermal, Chemical, other)

If other relevant wound care products or secondary dressings are required to be used in addition to the test product as part of standard of care, this must be recorded.

5.6. Potential compromising factors

The subjects are not allowed to receive antibiotics (also for other reasons than wound infection) 1 week upon inclusion. If, during the study period, the subject should acquire a condition requiring antibiotics, the condition must be registered as an AE and the antibiotic treatment must be registered as part of concomitant medication with start and end date.

5.7. Equipment

The wound area is measured by an [REDACTED] delivered by [REDACTED] that enables the PI or delegate to take a photo of the wound at every scheduled site visit. The photos are uploaded, stored, and analysed within an Imaging system delivered by [REDACTED] (Please refer to section 11 Data Management).

5.8. Randomisation Procedure

Not applicable

5.9. Blinding

Not applicable

5.10. Total expected duration of the clinical investigation

The dates below are approximate, and no subjects will be enrolled before all required approvals have been obtained. If changes are required, applicable EC and regulatory authorities will be notified.

First subject enrolled (07/2023)

Last subject enrolled (01/2024)

Last subject complete (01/2024)

Final report (02/2024)

6. Clinical Investigation population

The clinical investigation will be conducted in 50 subjects enrolled at multiple clinical investigation sites. The enrolment is competitive.

According to the sample size calculations (See section 10.4) 44 subjects are required to complete the investigation. Considering a drop-out rate of 10%, the required total number of subjects to be enrolled in the trial shall be 50.

6.1. Eligibility criteria

To be included in the investigation, the subjects must comply with the selection criteria described below.

6.1.1. Inclusion criteria

Table 1: Inclusion criteria

Inclusion criteria	Justification
--------------------	---------------

1. Has signed informed consent	To meet the Helsinki Declaration
2. Is between 18 - 65 years (both included)	To minimize the risk of non-device SAE
3. Is capable of following study procedure (assessed by investigator).	To ensure study protocol is followed in between site visits
4. Has a partial thickness burn wound	Selected indications
5. Has a burn wound that is infected or at risk of infection (assessed by investigator)	Selected indications (infected or risk of infection)
6. The size of burn (including both study wound and non study injuries) has a Total Body Surface Area (TBSA) less than 10% (assessed by investigator).	To minimize the risk of non-device related SAE
7. The wound should fit under a 20x30 cm dressing (600 cm ²) or smaller	To fit with the test product size
8. The shape and location of the wound should be suitable for photo capture (assessed by the investigator).	To minimize errors in the wound area measurement method
9. Has a wound that has medium to high level of exudate (assessed by the investigator)	According to the IFU
10. Is suitable to use the test product for wound treatment (assessed by the investigator).	No single treatment is completely successful for wound healing as complete wound healing depends on the type of wound, as well as the variation in the rate of production of wound exudates and the variation in the appearance of the wound surface in relation to wound type and healing phase

6.1.2. Exclusion criteria

Table 2: Exclusion criteria

Exclusion criteria	Justification
1. Is pregnant/breastfeeding	Vulnerable group
2. Is currently receiving or has within the past 60 days received radio- and/or chemotherapy (low doses radio- and/or chemotherapy is allowed for other indications than cancer if assessed by investigator not to influence study wound area)	The skin undergoes major changes because of radio- and/or chemotherapy, and therefore it can be more fragile during wound management

3. Known history of skin sensitivity to any components of the test dressings	According to IFU
4. >72 hours from time of injury	For the healing not to be influenced by the initial product used and to be comparable to other studies
5. Intake of antibiotics within one week before the start of the enrolment	To ensure any antimicrobial effect observed is due to the dressing and not the antibiotic
6. Use of chemical debridement	Chemical debridement can be used in a selected group of patients. Use of chemical debridement is excluded to ensure a homogeneous population in the study
7. Participation in any other clinical studies that can compromise this study treatment (assessed by the investigator).	To avoid bias.

6.1.3. **Pregnancy and breastfeeding**

All female subjects with childbearing potential (they have had at least one period during the last 12 months), must at V0 confirm that they are not pregnant or breastfeeding. Furthermore, they will be informed that no pregnancy is allowed during participating in the investigation.

If the subject becomes pregnant during the investigation, it is important, that the subject informs the Investigator or delegate immediately. The PI will then consider whether she should continue in the investigation.

6.2. **Recruitment and enrolment**

The recruitment of potential subjects will commence only once authorisation has been received from the respective EC and CA. Recruitment will occur through competitive enrolment in UK. The recruitment period from first subject enrolled to last subject enrolled will be approximately 5 months.

Recruitment will be via admitted patients in recruiting sites with hospitals and outpatient clinics, subject screening visits and advertisement in paper form and/or digital platforms.

6.3. **Screening of potential subjects**

If a subject is potentially eligible and interested in participating, written information about the investigation (Participant Information Sheet) will be provided to the subject to ensure they are given the opportunity to understand what the investigation is about. Subjects will have time to ask the PI, or delegate, any questions they may have. The subject information provides information to subjects about how to contact the local PI or a representative thereof if they wish to learn more about the investigation.

If a potentially eligible subject is interested in participating in the investigation a screening visit (V0) will be arranged. When arranging the visit, the subject must receive the Participant Information Sheet (PIS) and given adequate time to review it. The subject will receive both written and verbal information about the possibility of bringing a companion to the visit and to any possible subsequent visits.

The subject has the right to wait before deciding to participate. If/when the subject decides to participate, he/she will be asked to sign the Informed Consent Form. If a subject so desires, and it is certain that it is understood what the investigation entails, and the Informed Consent Form has been signed, the subject is considered enrolled/included in the investigation.

For subjects with more than one eligible wound, only a single wound can be included in the investigation.

The monitor will be in close contact with each site during the recruitment period. The PI, or delegate, at each site will notify the monitor when a subject is enrolled and all future planned visits.

When the Coloplast Clinical Manager becomes aware that 50 subjects have been included and the recruitment will stop.

Recruitment method	Hospital/Outpatient clinic	Advertising
Potential subjects	
Recruitment will go through hospital ward or outpatient clinic at the hospital site. Potential subjects are identified by the following searching criteria:
 
• Is 18 years or above• Is capable of following study procedure (assessed by investigator).• Has a partial thickness burn wound• Has a burn wound that is infected or at risk of infection (assessed by investigator)• The size of burn (including both study wound and non study injuries) has a Total Body Surface Area (TBSA) less than 20% (assessed by investigator).• The wound should fit under a 20x30 cm dressing (600 cm²) or smaller• The shape and location of the wound should be suitable for photo capture (assessed by the investigator).• Has a wound that has medium to high level of exudate (assessed by the investigator)• Is suitable to use the test product for wound treatment (assessed by the investigator).	
Recruitment may go through an advertisement.
 
The advertisement will state the contact information of relevant Principal Investigator(s) that potential subjects are asked to contact for further information.

First contact	
The potential subjects will be contacted by mail, phone call or contacted during a visit in at the hospital/ outpatient clinic.
 
If a subject is eligible and interested in participating in the investigation upon a short introduction, then written information about the investigation (Participation Information Sheet /Informed Consent Form) will be distributed to the subject.
 
The Principal Investigator or delegate will invite the subject to a Screening Visit (V0).
	
The potential subjects will mail or call the Principal Investigator.
 
If a subject is eligible and interested in participating in the investigation upon a short introduction, then written information about the investigation (Participation Information Sheet /Informed Consent Form) will be sent to the subject and the subject will be re-directed to a recruiting site near the subjects' home for a potential Screening Visit (V0).

Recruitment method	Hospital/Outpatient clinic	Advertising
Screening Visit (V0)	
At the scheduled Screening Visit (V0) the Principal Investigator or delegate will introduce the investigation and review the inclusion and exclusion criteria.
 
If the subject wishes to reconsider his/her participation at V0, the subject has the rights to wait minimum 24 hours before deciding on participation. If the subject hereafter decides to participate in the clinical investigation a Baseline Visit (V1) will be scheduled unless performed the same day as the Screening Visit.
 
The Screening Visit can be formed at the site or as a phone call.
 
If the subject does not meet the inclusion criteria or meet the exclusion criteria, this will be registered at the Subject Pre-Screening Log.
	
At the scheduled Screening Visit (V0) the Principal Investigator or delegate will introduce the investigation and review the inclusion and exclusion criteria.
 
If the subject wishes to reconsider his/her participation at V0, the subject has the rights to wait minimum 24 hours before deciding on participation. If the subject hereafter decides to participate in the clinical investigation a Baseline Visit (V1) will be scheduled unless performed the same day as the Screening Visit.
 
The Screening Visit can be formed at the site or as a phone call.
 
If the subject does not meet the inclusion criteria or meet the exclusion criteria, this will be registered at the Subject Pre-Screening Log.

Baseline Visit (V1)	If the subject decides to participate and it is certain that it is understood what the investigation entails, the subject will be asked to sign the PIS/ICF. When the PIS/ICF is signed the subject is considered included in the investigation.	If the subject decides to participate and it is certain that it is understood what the investigation entails, the subject will be asked to sign the PIS/ICF. When the PIS/ICF is signed the subject is considered included in the investigation.

6.4. Subject withdrawal criteria

The subject is allowed to withdraw from the investigation at any time for whatever reason without any consequences for their future treatment outside the clinical investigation. The PI may withdraw a subject from the investigation at any time if they judge it to be the subject's interest.

The PI must withdraw a subject from the investigation due to:

- Noncompliance with the CIP impacting the scientific integrity of the investigation.
- If subject's safety and wellbeing is compromised by further participation.
- Subjects lost to follow-up. At least three documented attempts will be made to verify subjects lost to follow-up.

Withdrawn subjects will not be replaced by new subjects.

A subject who is withdrawn from the investigation, for any reason, will be encouraged to contact the PI if problem arises, that the subject believes are related to the clinical investigation. Subject who has not experienced any adverse events, will not be followed up. For subjects who experience adverse events see section 18.1.

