5.1. General

The clinical investigation is a non-comparative, one-armed, open-labelled, multi-centre study. The study is planned to be conducted in UK.

The total study duration for the subject will be approximately two weeks, consisting of a two-week test period and 4 study visits (V0/V1, V2 and V3)

In total 50 subjects will be included in the investigation. Eligible subjects are invited to a Screening Visit (V0). Screening visit (V0) and Baseline visit (V1) can be combined and performed on the same day. If subject wishes to reconsider his/her participation at V0, the subjects must be given at least 24 hours to consider their participation. V0 can be done remotely.

At V0 the subject will be informed about the investigation, where the PI or delegate will give a detailed information about the requirements, the content and what it involves participating in the investigation. See section 6.2 for recruitment.

Informed Consent will be signed at the Baseline Visit (V1) and obtained before any study-related activities are initiated. Informed consent must be signed within 72 hours from burn injury.

Subjects will use the investigational test product in a 2-week test period (+/- 2 days) and have a scheduled visit once per week, visit 2 (V2) and visit 3 (V3). V3 will also terminate the 2-week study period unless a situation occurs where a subject terminates earlier than expected.

Withdrawn subjects must be encouraged to complete the Termination visit V3, regardless of the reason for withdrawal.

If dressing change is needed due to a clinical need between the weekly scheduled study site visits, additional visits can be performed. See section 7.2 for Dressing changes between study site visits.

If visits are needed due to circumstances related to a specific issue, an unscheduled visit can be performed. See section 7.3 for Unscheduled visits.

If the wound is evaluated by PI or delegate to be healed before or at the termination visit V3 subjects will be terminated according to termination – Wound healed. See section 7.4 Wound healed.

[figure not shown]
[figure not shown]

Figure 1: Study design CP357

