10.2. Analysis of endpoints, individual questions, and assessments

All collected data including withdrawals will be accounted for in listings. All endpoints and baseline information will be listed and summarized by descriptive statistics. The summaries will be done in total and by the different population groups. Summaries and listing will include both safety/ITT and FAS population.

Summary statistics for continuous variables are presented with N, Mean, SD (standard deviation), Median, Min and Max, where N denotes the number of subjects contributing with non-missing data. For discrete variables, summary statistics are presented with N and percentage, where percentage is based on the total number of subjects/observations with non-missing data.

Other summaries and analyses can be made, if relevant.

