10.3. Analysis of primary endpoint

The primary endpoint proportion of wounds healed will be analyzed using a binomial proportion test.

The purpose of the primary analysis is to show non-inferiority to the performance of the similar product Aquacel Ag (a silver containing gelling fiber) on proportion of wounds healed, 77 %, with a non-inferiority margin of 20 %. (1)

Since the performance of Aquacel Ag is a fixed proportion, this is equivalent to testing whether the performance of Biatain Fiber Ag is superior to $77 - 20 = 57$ %.

Let the null hypothesis and the alternative hypothesis be defined as:

- $H_0: \mu_{\text{Biatain Fiber Ag}} \leq 57$ % wounds healed
- $H_1: \mu_{\text{Biatain Fiber Ag}} > 57$ % wounds healed

Where Non-inferiority will be demonstrated if H_0 is rejected.

This will be done using the proc freq procedure with a binomial test and if the lower limit of the 95 % confidence interval is above 57 % H_0 is rejected, and the success criteria fulfilled.

Furthermore, as a conservative estimate, a sensitivity analysis will be performed on the primary endpoint, where patients lost to follow-up, or otherwise missing information, will be considered not healed in regards to their wound.

The exploratory endpoints will be analysed descriptively and presented with confidence intervals.

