10.4. Sample size

The primary endpoint is proportion of wounds healed and the sample size calculation is based on a proportion of 77 %. The design is a non-inferiority design, where we want to show noninferiority with a margin of 20 %.

This gives

The POWER Procedure
Z Noninferiority Test for Binomial Proportion

Fixed Scenario Elements	
Method	Normal approximation
Number of Sides	U
Null Proportion	0.77
Margin	-0.2
Alpha	0.025
Binomial Proportion	0.77
Nominal Power	0.8
Variance Estimate	Null Variance

Computed N Total	
Actual Power	N Total
0.801	44

Meaning a total of 44 completers gives a sufficient (80%) power. Accounting for dropouts (10%) gives us 50 subjects.

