10.5. Level of significance and power

The study is designed with a power of 80 % and testing of the primary analysis will be done using a one-sided 0.025 significance level. No other statistical test as pre-planned.

11. Data management

Data management and the final statistical analyses of all measurements described in this protocol are carried out by Clinical Strategies, Coloplast A/S.

Data will be collected through an electronic data capturing (EDC) system on electronic Case Report Form (eCRF), a secure, internet-based case report form. This system will be used to record all subject information collected in the investigation for secure data tracking and centralised data monitoring ("remote monitoring") done by monitors, as defined in the monitoring section.

The system is designed to be compliant with the FDA requirements of 21 CFR part 11. It is a validated data management system allowing only qualified and trained personnel to enter the system. The system has full audit trail and electronic signature.

The data management system has restricted role-based access control. The principal investigator or delegate must be trained in the system prior to getting access. The sponsor will be responsible for training the investigator or delegate, in completion of the eCRF. The training is web-based and must be completed before access to the investigation is granted. Training will be documented in the data management system. The data manager will also demonstrate the system on a virtual meeting. Only the principal investigator, or delegate, will be authorised to enter data in the eCRF.

The monitor, using his/her personal login information shall verify all critical data points against the source documents and issue electronic queries for the authorised clinical site personnel to respond, as defined in the monitoring section.

A critical quality control will be performed by the sponsor's data management team and queries issued where needed. Such queries must be resolved by the site personnel.

The principal investigator, using his/her personal login information, shall sign each eCRF.

Automated, real-time access to the data enable control on study compliance and safety assessments.

A full audit trail ensures, that each user's (site personnel, monitor, sponsor, data manager) access to and actions in the system is tracked.

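### Sections 5.1 and 6.4 leave unclear whether and when a withdrawn subject's healing outcome is collected, and 10.3 has no missing-data rule for the primary test, so unhealed withdrawals could leave the denominator

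*Combined protocol and SAP*

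**What the plan says.** Section 5.1 (General): "Withdrawn subjects must be encouraged to complete the Termination visit V3, regardless of the reason for withdrawal". V3 is thus encouraged for every withdrawn subject but is not compulsory. Its timing after withdrawal is not given.

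Section 6.4 (Subject withdrawal criteria): "Subject who has not experienced any adverse events, will not be followed up". The sentence carries no limit of time or purpose. It stands between an invitation to contact the investigator if problems arise and a reference to section 18.1 for subjects with adverse events. Section 18.1 only defines an adverse event. Section 6.4 also says that withdrawn subjects are not replaced.

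On analysis, section 10.1 bases the statistical analyses on the full analysis set, meaning exposed subjects with information on a primary or secondary endpoint. Section 10.2, on summary statistics for discrete variables, says that "percentage is based on the total number of subjects/observations with non-missing data". Section 10.3 sets the success rule: "if the lower limit of the 95 % confidence interval is above 57 % H_0 is rejected". It adds a sensitivity analysis in which missing outcomes count as not healed, and does not say how they enter the primary test itself.

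**The concern.** Take a subject whose burn is progressing poorly and who is withdrawn without an adverse event. Section 5.1 has the site encourage attendance at V3. Section 6.4, the section a site is likely to open when a subject withdraws, can be read as ending contact. Section 7 rules out study wound assessments at unscheduled visits and at dressing changes between visits. After V2 the outcome therefore depends on V3 or on the wound-healed termination visit. Subjects who heal early leave through that termination visit with the outcome recorded, so early healers are unlikely to be the ones lost.

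If unhealed subjects are the ones lost and the primary test uses observed outcomes only, the healed proportion rises. With one arm and a fixed 57% threshold, no control arm offsets this, and the error runs towards declaring non-inferiority.

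**Working it through.** **Inputs.** Significance level: "testing of the primary analysis will be done using a one-sided 0.025 significance level" (10.5). Power: "The study is designed with a power of 80" per cent (10.5). Assumed rate: "the sample size calculation is based on a proportion of 77" per cent (10.4). Margin: "with a non-inferiority margin of 20" points (10.3), so the null is 77 − 20 = 57%. The plan has 44 completers and 50 enrolled at 10% drop-out (10.4).

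**The plan's own figure.** One-sample Z test with null variance:

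n = [(1.960·√(0.57·0.43) + 0.842·√(0.77·0.23)) / 0.20]² = 43.86, so 44, with power 0.801. This reproduces. For drop-out, 44/0.9 = 48.9, so 49, against the stated 50. The sample size is not in dispute.

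**Success thresholds.** This is the smallest number healed whose Clopper-Pearson lower 95% limit exceeds 57%: 36/50, 35/48, 34/47, 33/45.

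**One data set, two denominators.** Suppose 33 are healed and 5 of 50 outcomes are missing.
- Observed cases: 33/45 = 73.3%, lower limit 58.1%, success.
- Missing counted as not healed: 33/50 = 66.0%, lower limit 51.2%, failure.

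Wald limits (60.4% and 52.9%) give the same two conclusions.

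**Chance of success at a true rate of 57%, with k of 50 lost.** The threshold is t = 36, 35, 34, 33 for k = 0, 2, 3, 5.
- Model A: exactly k unhealed subjects are removed, P[Bin(50, 0.57) ≥ t].
- Model B: all lost subjects are unhealed and the rate among the rest is rescaled, P[Bin(50−k, 0.57·50/(50−k)) ≥ t].
- Model C: loss is unrelated to healing, P[Bin(50−k, 0.57) ≥ t].

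| k lost | A | B | C |
|---|---|---|---|
| 0 | 2.1% | 2.1% | 2.1% |
| 2 | 4.2% | 3.7% | 1.7% |
| 3 | 7.5% | 6.5% | 2.2% |
| 5 | 12.6% | 10.6% | 1.8% |

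A and B are two versions of the worst case, and C is the benign case. Section 10.3 does not name the type of interval. With Wald limits the chance at k = 0 is already 4.2% (threshold 35/50), and under model B with k = 5 it is 17.7% (threshold 32/45).

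**Price of counting missing as not healed.** If 77% of the 45 observed heal and 5 are missing, the chance of success is P[Bin(45, 0.77) ≥ 33] = 78.1% on observed cases. It is P[Bin(45, 0.77) ≥ 36] = 39.3% when the 5 count as not healed out of 50.

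**The case against.** A reader might infer that 5.1 and 6.4 give opposite instructions for the same subject. The documents do not support that. The sentences around the 6.4 statement concern problems and adverse events after leaving the study, and section 18.5 uses the same expression for adverse events still ongoing at the termination visit. On that reading the sections fit together: V3 first, then no further contact unless there was an adverse event. This stands, and the point is therefore an ambiguity.

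Nor does 6.4 alone cause the loss. V3 is only encouraged and a subject may decline it, so outcomes could be missing even without the 6.4 sentence. V2 also records whether the wound is healed, so a subject withdrawn after V2 may be in the full analysis set with a recorded negative answer, although 10.3 does not say how that would be used. Section 10.2 describes summary statistics, so exclusion from the primary denominator is an inference. It is a natural one: the sensitivity analysis would be redundant if the primary test already counted missing as not healed.

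That sensitivity analysis would report the 33/50 result and make the discrepancy visible. This is partial protection only, because the success criterion is attached to the primary test.

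Finally, nothing in the documents shows that withdrawal without an adverse event goes with poor healing. It is plausible but assumed.

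**Conclusion.** The point holds as an ambiguity with a plausible bias towards success. Section 6.4 lacks a limit to the period after termination, 5.1 lacks a time for the withdrawn subject's V3, and 10.3 lacks a missing-data rule for the primary test. An assessment on the day of withdrawal would not settle healing within 14 days.

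In the worst case the chance of wrongly declaring success rises from 2.1% to 6.5–7.5% with 3 lost and to 10.6–12.6% with 5 lost, which is the planned 10% drop-out. This assumes a true rate of 57% in all 50, every lost subject unhealed and without a usable V2 record, an observed-case primary test, and exact limits. If loss is unrelated to healing, the figure with 5 lost is 1.8% and there is no inflation. A reader might take the upper figures as the expected error rate; the documents do not support that, because they give no link between withdrawal and healing.

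**What to change.** 1. In 6.4, limit the sentence on no follow-up to the period after V3 and cross-refer to 5.1.
2. In 5.1, state that every withdrawn subject who agrees, with or without an adverse event, has the yes/no healing assessment and the photo at day 14 (±2 days) after V1. Record the date and reason the test product was stopped, since the plan does not separate stopping the product from leaving the study.
3. In 10.3, state that treated subjects whose outcome is still missing count as not healed in the primary test. This covers those who decline V3, whom the first two changes do not reach.
4. In 10.3, state how healing after the product was stopped is counted. Healing under other care, if counted as success, could itself favour the product.

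Cost: a few sentences and a few more contact attempts. V3 is already scheduled for every subject. The healing rate may come out slightly lower. The third change also costs power for each outcome that stays missing, as the fall from 78.1% to 39.3% with 5 missing shows, so the day-14 assessment is the more valuable part.
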